5 STUDY TREATMENTS AND MANAGEMENT

5.1 Description of Study Drug, Dose, and Administration

5.1.1 Description of Study Drug

Study drug is defined as miricorilant tablet, 150 mg or placebo for miricorilant tablet, 150 mg. Description of the study drug, including packaging and storage, is described in [Table 1](#).

Table 1 Study Drug: Description, Packaging, and Storage

Specifications	Miricorilant	Placebo
[REDACTED]	[REDACTED]	[REDACTED]
Supplied	Tablets, 42-count in child-resistant blister packaged cards and labeled per country requirement.	Tablets, 42-count in child-resistant blister packaged cards and labeled per country requirement.
Unit Dose Strength	Miricorilant tablet, 150 mg	Placebo for miricorilant tablet, 150 mg
Dose levels	600 mg and 900 mg	N/A
Missed doses	If the patient remembers they missed a dose within 12 hours of their normally scheduled dosing time, then they should take their daily dose of study drug and then resume normal schedule	If the patient remembers they missed a dose within 12 hours of their normally scheduled dosing time, then they should take their daily dose of study drug and then resume normal schedule
Dispensing study drug	Dispense to patients at the visits specified in Appendix A	Dispense to patients at the visits specified in Appendix A
Storage	Store as follows: 
 • In a secure location • At 20°C–25°C (68°F–77°F), excursions permitted to 15°C–30°C (59°F–86°F) • Out of sight and reach of children 	Store as follows: 
 • In a secure location • At 20°C–25°C (68°F–77°F), excursions permitted to 15°C–30°C (59°F–86°F) • Out of sight and reach of children

Procedures for inventory, reconciliation, and destruction or return of study tablets are provided in [Section 11.6](#).

5.1.2 Administration of Study Drug

Patients will be randomized in a 1:1:1 ratio to 600 mg miricorilant, 900 mg miricorilant, or placebo. Study drug will be administered once daily, orally with 8 oz (240 mL) of water, along with food.

Patients will be instructed to take a total of 6 tablets at approximately the same time each day.

- Those in the 600 miricorilant group will take 4 miricorilant tablets and 2 placebo tablets.
- Those in the 900 miricorilant group will take 6 miricorilant tablets.
- Those in the placebo group will take 6 placebo tablets.

For the week 6 visit, patients will be instructed to not take their daily study drug prior to the visit, but to bring their study drug to the site with them so that the study drug can be administered at the site.

5.2 Non-Investigational Medicinal Agent

Not applicable.

5.3 Dose Modification

5.3.1 Dose Reduction

No dose modification will be allowed.

5.3.2 Dose Interruption and/or Discontinuation: General Criteria

Study treatment should be temporarily interrupted if deemed medically necessary by the Investigator. On interrupting the study treatment, the Investigator should notify the Corcept Medical Monitor. Before restarting study treatment, the Investigator must obtain approval from the Corcept Medical Monitor. If the event that necessitated treatment interruption recurs after study treatment is restarted, the patient should be permanently discontinued from study treatment. In addition, patients will be permanently discontinued from study treatment if they experience any of the criteria listed for stopping treatment in [Table 2](#).

5.3.3 Dose Interruption and/or Discontinuation: Special Safety Events

Based on the mechanism of action of miricorilant, there is a theoretical risk of excessive GR antagonism and excessive MR antagonism. Thus far in clinical experience with miricorilant in healthy volunteers as well as in patients with AIWG, an increased incidence of excessive GR or MR antagonism has not been observed. Excessive GR antagonism could manifest as a combination of findings such as weakness, tiredness, dizziness, orthostatic hypotension, hypoglycemia, dehydration, nausea, vomiting, diarrhea, and muscle aches. Excessive MR antagonism could manifest as hyperkalemia, dehydration, and hypotension; hypotension may be seen in the absence of antihypertensive medication. These symptoms should be monitored throughout the duration of the clinical trial both during Treatment and in the Follow-up period. If excessive GR and/or MR antagonism is suspected, patients should discontinue the study medication, and administration of intravenous fluids, and intravenous or oral hydrocortisone should begin without delay. [REDACTED]

[REDACTED] Symptoms should continue to be monitored even after the last dose of study medication in the follow-up period; intravenous fluids and hydrocortisone should be administered as clinically appropriate to reverse excessive GR and MR antagonism.

At each study visit starting with the Baseline visit, patients will be evaluated for signs and symptoms of excessive GR or MR antagonism. For patients who experience symptoms, the actions outlined in [Table 2](#) should be taken.

Guidelines for temporarily interrupting and restarting and for permanently discontinuing study treatment due to other safety events (hyperkalemia; hypotension; excessive miricorilant

exposure; suspected liver injury, and significant trauma, surgery, or medical illness) are outlined in [Table 2](#).

For assessment of suspected liver injuries, baseline values for ALT, AST and total bilirubin will be the mean of all values obtained from Screening through Day 1. Please refer to the laboratory manual or individual subject laboratory report for gender- and age-specific references.

Elevations of ALT or AST are defined as a baseline ALT or AST $<ULN$ that increased to $>3\times ULN$ on treatment, or a baseline ALT or AST $>ULN$ and on-treatment $>2\times$ baseline. Elevations should be confirmed with repeat testing within 48 to 72 hours. If confirmed, and if no other cause of laboratory abnormality is immediately apparent, the Corcept Medical Monitor is to be notified. Patients with ALT or AST elevations must be placed into close observation (see [Table 2](#)).

Table 2 Criteria for Dose Modification or Discontinuation Due to Special Safety Events

Safety Event	Criteria for Interrupting and Restarting Study Treatment and Patient Management	Criteria for Stopping Study Treatment
Excessive GR or MR antagonism	
Criteria: signs and symptoms of excessive GR and MR antagonism (Section 1.5)
 
Management:
 
 • Immediately interrupt miricorilant treatment for ≥ 5 days and start standard supportive care, including intravenous fluids as indicated. • If appropriate, administer supplemental glucocorticoids given in high doses to overcome the GR antagonism produced by miricorilant. Initially, consider intravenous hydrocortisone, followed by additional intravenous or oral doses once or twice daily for 1 to 3 days and tapered thereafter, depending on clinical response. In some cases, higher doses of hydrocortisone for longer periods of time may be required. • If the patient has been receiving treatment with an MR antagonist, consider discontinuing it, particularly in the presence of hypotension. • Restart miricorilant treatment only if the workup reveals an alternative cause for symptoms of possible excessive GR/MR antagonism and after consultation with the Corcept Medical Monitor. 	
A combination of the following Grade 3 or higher events: fatigue, anorexia, nausea, and vomiting (associated with decreased oral intake), and abdominal pain.

Hypotension	
Criteria: development of hypotension while on study drug.
 
Management:
 
 • Confirm the diagnosis by office BP monitoring and orthostatic BP measurements. • Examine patient and check potassium levels. • If appropriate, advise the patient to hydrate orally with electrolyte containing hydration (e.g., Gatorade or Pedialyte). Hypotension can also be supported with intravenous hydration with isotonic fluids. • Patients who have hypotension should have any antihypertensive medications and diuretic medications discontinued as appropriate. • Interrupt miricorilant if SBP <100 mm Hg or if DBP <60 mm Hg or if orthostatic hypotension is present or if patient requires treatment with intravenous fluids. • Restart miricorilant only if hypotension is transient and reversible and not related to study medication, and after consultation with the Corcept Medical Monitor. 	
Systolic BP <100 mm Hg or diastolic BP <60 mm Hg (as confirmed by office BP measurements) or orthostasis, despite the discontinuation of antihypertensive medications and intravenous and oral hydration.

Safety Event	Criteria for Interrupting and Restarting Study Treatment and Patient Management	Criteria for Stopping Study Treatment
Hyperkalemia	Criteria: development of hyperkalemia during the study. Management: 
 • Verify hyperkalemia and normal renal function. • Obtain ECG for evaluation of hyperkalemia. • Interrupt miricorilant if hyperkalemia is severe (>6.0 mEq/L) or if renal function is impaired. • As medically indicated, initiate treatment for hyperkalemia. • Restart miricorilant only if the underlying cause of hyperkalemia is transient and correctable and after discussion with the Corcept Medical Monitor. 	Severe (>6.0 mEq/L) hyperkalemia. Confirmed ECG abnormalities including peaked T waves, shortened QT interval, ST segment depression, prolonged PR interval, flattened p wave, widened QRS, amplified R wave, or intraventricular/fascicular/bundle branch blocks. Underlying renal disease.
Suspected liver injury	Criteria: development of suspected liver injury while on study drug Management: 
 • Repeat liver biochemistries (ALT, AST, total bilirubin) within 48 to 72 hours of results. • Obtain a more detailed history of symptoms and prior or concurrent disease and a history of concomitant drug use (including nonprescription medication and herbal and dietary supplement preparations). • Obtain a history of exposure to environment chemical agents. • Rule out other causes of liver disease as needed, if required in the opinion of the Investigator. • Obtain additional tests to evaluate liver function, as appropriate (e.g., INR, direct bilirubin). • Continue to monitor the liver biochemistry at least twice weekly. Frequency can decrease to once a week or less if abnormalities stabilize or study drug has been discontinued and the patient is asymptomatic. • During the period of close observation, study drug can be continued if desired at the discretion of Corcept Medical Monitor and Investigator. 	For patients with elevated baseline AST, ALT, total/direct bilirubin (>ULN) 
 • If baseline value was <2×ULN, discontinue if ALT or AST increases to >5×baseline. • If baseline value was ≥2×ULN but <5×ULN, discontinue if ALT or AST increases to >3×baseline. • If baseline value was ≥5×ULN, discontinue if ALT or AST increases to >2×baseline. • If ALT or AST increases to >2×baseline value and the increase is accompanied by a concomitant increase in total bilirubin to >2×baseline value or an increase in INR by >0.2. If a patient has Gilbert’s syndrome, ≥35% of total bilirubin must also be direct bilirubin. • In any patients with signs and symptoms of fatigue, nausea, vomiting, right upper quadrant pain or tenderness, fever, rash, and/or eosinophilia (>5%).

Safety Event	Criteria for Interrupting and Restarting Study Treatment and Patient Management	Criteria for Stopping Study Treatment
Significant trauma, surgery, or medical illness at any time during the study (through 2 weeks after last dose)	Management: 
 • As medically indicated, interrupt miricorilant treatment and provide supplemental hydrocortisone to offset the GR antagonism even in patients not experiencing signs and symptoms of excessive antagonism. • After resolution of the physiological stress associated with the event and if still within the Treatment Period, resume miricorilant. 	Patient does not recover from the significant trauma, surgery, or medical illness within the Treatment Period.

Abbreviations: ALT, alanine aminotransferase; AST, aspartate aminotransferase; BP, blood pressure; DBP, diastolic blood pressure; DILI, drug-induced liver injury; ECG, electrocardiogram; GR, glucocorticoid receptor; INR, international normalized ratio; MR, mineralocorticoid receptor; SBP, systolic blood pressure; ULN, upper limit of normal.

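### Protocol Table 2, Hyperkalemia row: potassium >6.0 mEq/L triggers both a restartable interruption and an unqualified permanent stop, and nothing says which governs

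*Protocol*

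**What the plan says.** Protocol Section 5.3.3 presents Table 2 as covering two separate outcomes for hyperkalemia and other safety events: pausing and resuming study drug, and ending it for good. The Hyperkalemia row has one cell for each.

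- **Management cell.** The first step is "Verify hyperkalemia and normal renal function". A later bullet reads "Interrupt miricorilant if hyperkalemia is severe (>6.0 mEq/L) or if renal function is impaired". The last reads "Restart miricorilant only if the underlying cause of hyperkalemia is transient and correctable and after discussion with the Corcept Medical Monitor".
- **Stopping cell.** The first entry is "Severe (>6.0 mEq/L) hyperkalemia". The other two entries are confirmed ECG abnormalities and underlying renal disease.

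Section 5.3.2 gives the stopping cell its force: "patients will be permanently discontinued from study treatment if they experience any of the criteria listed for stopping treatment in" Table 2. It also says "Before restarting study treatment, the Investigator must obtain approval from the Corcept Medical Monitor", and adds a general recurrence rule: "If the event that necessitated treatment interruption recurs after study treatment is restarted, the patient should be permanently discontinued from study treatment".

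**The concern.** The same potassium value sits in both cells. One cell treats it as the start of a pause that may end in restart; the other, through Section 5.3.2, treats it as the end of treatment. Nothing about persistence, recurrence or cause separates the two.

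Section 1.5 names hyperkalemia as a possible effect of excessive MR antagonism, so this rule concerns a mechanism-related risk of the study drug. At stake is whether a patient who has had a verified value >6.0 mEq/L may be re-exposed, and whether the Medical Monitor has a rule for deciding. Section 11.9 bars protocol waivers and lets sponsor staff acknowledge but not approve deviations, so the gap cannot be closed by discretion. A restart that fits the management cell would still depart from Section 5.3.2.

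**Working it through.** No figure in the plan needs reproducing. The check sets the two cells against each other, case by case.

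| Case | Management cell | Stopping cell with 5.3.2 | Consistent? |
|---|---|---|---|
| Verified K >6.0, transient correctable cause, no confirmed ECG abnormality, no underlying renal disease | Interrupt; restart open after discussion | Permanent stop | **No** |
| Verified K >6.0, cause not correctable | Interrupt; restart conditions not met | Permanent stop | Yes |
| Verified K >6.0 with a confirmed ECG abnormality or underlying renal disease | Interrupt | Permanent stop on another ground as well | Outcome settled by the other criterion |
| Reading >6.0 that does not verify | Interrupt; restart open | Literally met, since the entry does not require verification | Unclear |
| K ≤6.0, renal function impaired but no underlying renal disease or confirmed ECG abnormality | Interrupt; restart open | Not met | Yes |

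Four readings might remove the conflict in the first case.

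1. *The three stopping entries apply jointly.* They are separate sentences, and Section 5.3.2 applies to any one criterion.
2. *The cells describe a sequence.* The Hypotension row shows how the protocol writes one. It repeats its blood-pressure limits in both cells, but its stop applies only when the problem persists after antihypertensives are withdrawn and fluids are given. The Hyperkalemia row has no such wording.
3. *Verification separates them.* It confirms the value. It does not say which cell governs a confirmed value.
4. *The recurrence rule separates them.* Section 5.3.2 gives recurrence as one ground for permanent discontinuation and Table 2's stopping criteria as an additional one. Neither limits the other.

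**Exposure in dispute for one patient.** Planned dosing is 12 × 7 = 84 days. Chemistry, which includes potassium (Table 5), is drawn at every treatment visit (Section 7.3). Before Week 12 these fall on Days 15, 29, 43, 57 and 71. Days dosed before each visit = day − 1 = 14, 28, 42, 56 and 70. Days left = 84 − days dosed = 70, 56, 42, 28 and 14. These are loose upper bounds: the row states no interruption length, so none is subtracted. The ±2-day windows and unscheduled tests are ignored. Section 5.8 has visit-day doses taken in clinic after the blood draw, so at least one more dose would normally precede the result. The figures say nothing about how often the event occurs or what harm follows.

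**The case against.** The strongest defence is that the row can be read as a whole. The restart bullet is an *only if* condition: it sets necessary conditions and grants no entitlement. Section 5.3.2 is mandatory. On that reading the site interrupts at once, verifies, and stops if the value is real. Restart then serves interruptions for impaired renal function and readings that do not verify. This defence stands in part. A reader might infer that the row is irreconcilable or its restart bullet empty; the fifth case above shows otherwise. The defence also makes the permanent stop the more natural resolution. But the restart bullet speaks of the underlying cause of hyperkalemia and follows a trigger defined by potassium >6.0 mEq/L, so a reader can fairly take it to cover that trigger. No text says it does not.

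A reader might also infer that sites are free to re-expose patients. They are not: every restart needs Medical Monitor approval. Where excessive GR or MR antagonism is suspected, Section 5.3.3 says to discontinue. The first row of Table 2 requires an interruption of at least 5 days and allows restart only if the workup finds another cause. Reporting of Grade 3 or higher findings within 24 hours, exclusion of patients with eGFR ≤60, and IDMC review are further limits. They reduce the risk. They do not tell the Medical Monitor which cell governs an isolated potassium value, since Section 5.3.3 lists hyperkalemia as an event of its own.

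The idle recurrence rule is weak evidence. It is a general rule for all interruptions, and having nothing to do for one trigger does not prove a conflict.

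Finally, SAP Section 9.8 says the study was terminated early for safety observations, and a reader might connect this row to that. The section does not name hyperkalemia, so the documents do not support the link.

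**Conclusion.** The inconsistency is real and narrow. It bites for a patient with verified potassium >6.0 mEq/L, a cause judged transient and correctable, and no other stopping criterion. For that patient the restart provision conflicts with the permanent stop of Section 5.3.2, and neither document gives precedence. The number of such patients is not stated and cannot be derived. No endpoint, sample size or power figure is affected.

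The conclusion assumes that the three stopping entries are alternatives, as the wording of Section 5.3.2 indicates, and that no unstated precedence rule exists. It should be corrected because the rule concerns re-exposure after a mechanism-related safety event. Given the early termination, the practical value lies mainly in any reuse of the table.

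**What to change.** Follow Section 5.3.2, which is mandatory and the safer of the two rules. Make three edits in the Hyperkalemia row:

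1. **Stopping cell:** *Verified (repeat-test) severe (>6.0 mEq/L) hyperkalemia.* Without this qualifier, a spurious reading would still literally meet a permanent stop while the edited restart bullet allowed restart.
2. **Interrupt bullet:** *Interrupt miricorilant at once if potassium is >6.0 mEq/L, pending a prompt repeat test, or if renal function is impaired; if >6.0 mEq/L is verified, discontinue permanently. A repeat taken after potassium-lowering treatment does not overturn the first value.*
3. **Restart bullet:** *Restart only if potassium >6.0 mEq/L was not verified, no other stopping criterion is met, the underlying cause is transient and correctable, and the Corcept Medical Monitor has been consulted.* The approval requirement in Section 5.3.2 continues to apply.

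Restart then remains for readings that do not verify and for impaired renal function that is not underlying renal disease.

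The alternative is to copy the Hypotension row and stop only if potassium stays high despite treatment. That would keep the restart option but loosen the present mandatory stop, so the sponsor should choose it only if that was the intent, and should say so.

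Cost: wording in one row, with no change to scheduled visits or sample size. The row already asks for verification; the edit specifies a repeat test. The downside is that a patient with a verified value >6.0 mEq/L from a correctable cause can no longer restart.

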4.1 Inclusion Criteria

Patients eligible for enrollment into this study must meet the following criteria:

1. Have provided informed consent.
2. Are men or women ≥ 18 to ≤ 75 years old.
3. Have a diagnosis of presumed NASH with fibrosis defined as meeting all of the following criteria:
 - a. Either:
 - (i) A historical liver biopsy within 1 year of Screening showing NASH, NAFLD Activity Score (NAS) ≥ 4 , and F1 to F3 fibrosis
OR
 - (ii) The following two criteria based on non-invasive measurements:
 - AST > 17 U/L for women and AST > 20 U/L for men AND
 - FibroScan liver stiffness measurement ≥ 8.5 kPa and Controlled Attenuation Parameter (CAP) ≥ 300 dB/m in the 3 months prior to Screening or at Screening
 - b. MRI-PDFF with $\geq 10\%$ steatosis
 - c. Presence of 2 or more components of metabolic syndrome: type 2 diabetes treatment or fasting blood glucose ≥ 126 mg/dL, BMI ≥ 30 kg/m², hypertension treatment or blood pressure $\geq 130/85$, history of dyslipidemia, or waist circumference ≥ 102 cm (40 in) in men and ≥ 88 cm (35 in) in women
4. Must have consistent ALT and AST Baseline measurements, established by 2 samples obtained at least 4 weeks and no more than 6 months apart. At least one of the values must be derived from Screening safety labs; historical results within 6 months of Screening may be used to provide the second value for eligibility. Unless both samples are $\leq 1.5 \times$ the upper limit of normal (ULN), to be eligible for study entry, the difference between the first and second measurement of ALT and AST should be $\leq 50\%$. A third sample may be repeated if the variability between the first 2 values exceeds the 50% limit. If the third sample exceeds the 50% limit (compared with the first result), the patient is not eligible.
5. Patients who are taking lipid-modifying therapies must be on stable doses for at least 3 months prior to Screening and unlikely to change the dose during the study (for patients taking statin medications, please see additional restrictions in exclusion criterion #15).
6. Agree to use highly effective methods of contraception throughout the study and for at least 28 days after the last dose of assigned treatment, for both male patients and female patients of childbearing potential; (see Section 4.6.4 and 4.6.5 for details).

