 - c. Total bilirubin >1.3 mg/dL (except for patients who have Gilbert's syndrome; see exclusion criterion #21f)
 - d. History of esophageal or gastric variceal bleedings, ascites, or hepatic encephalopathy
- 22. Have any other chronic liver disease:
 - a. Hepatitis B as defined by presence of hepatitis B surface antigen
 - b. Hepatitis C as defined by presence of hepatitis C virus (HCV) antibody and positive HCV RNA. Documented cured HCV infection is acceptable if >3 years from Screening visit
 - c. History of current active autoimmune hepatitis

- d. History or evidence of primary biliary cholangitis
 - e. History or evidence of primary sclerosing cholangitis
 - f. History or evidence of Gilbert's syndrome if direct bilirubin is elevated (in addition to total bilirubin ≥ 2) or evidence of hemolysis contributing to elevated total bilirubin
 - g. History or evidence of Wilson's disease
 - h. History or evidence of alpha-1-antitrypsin deficiency
 - i. History or evidence of hemochromatosis
 - j. History or evidence of drug-induced liver disease, as defined on the basis of typical exposure and history
 - k. Known bile duct obstruction
 - l. Suspected or proven liver cancer
 - m. Any other type of liver disease other than NASH
23. Have a history of biliary diversion.
 24. Are seropositive for human immunodeficiency virus.
 25. Have a history of cancer within the last 3 years (in situ carcinomas, cutaneous basal cell or squamous cell cancer resolved by excision are not excluded).
 26. Have contraindications to magnetic resonance imaging (MRI).
 27. New York Heart Association class III or IV heart failure, or known left ventricular ejection fraction $< 30\%$.
 28. Uncontrolled hypertension (either treated or untreated) defined as systolic blood pressure > 160 mm Hg or a diastolic blood pressure > 100 mm Hg at Screening.
 29. Uncontrolled cardiac arrhythmia, including confirmed QT interval corrected using Fridericia's formula (QTcF) > 450 msec for males and > 470 msec for females at the Screening ECG assessment.
 30. Myocardial infarction, unstable angina, percutaneous coronary intervention, coronary artery bypass graft, or stroke within 3 months prior to Screening.
 31. Active substance abuse, including inhaled or injected drugs, within 1 year prior to Screening.
 32. Have any clinical condition or significant concurrent disease judged by the Investigator to complicate the evaluation of the study treatment.

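### Protocol Table 2 sets no required stop on ALT or AST alone for a patient whose baseline liver tests are all normal

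*Protocol*

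**What the plan says.** Section 5.3.2 of the protocol gives the stopping column of Table 2 its force: meeting any criterion there means permanent discontinuation.

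The liver row of that column is introduced by "For patients with elevated baseline AST, ALT, total/direct bilirubin (>ULN". Five bullets follow:

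- Three act on ALT or AST alone: above 5×baseline when baseline is under 2×ULN, above 3×baseline when it is from 2 to under 5×ULN, and above 2×baseline when it is 5×ULN or more.
- One is a combined rule: ALT or AST above 2×baseline, together with total bilirubin above 2×baseline or an INR rise of more than 0.2.
- One is symptom-based and begins "In any patients with signs and symptoms of fatigue, nausea, vomiting, right upper quadrant pain or tenderness"; it also covers fever, rash and eosinophilia.

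Section 5.3.3 sets the reference value: "baseline values for ALT, AST and total bilirubin will be the mean of all values obtained from Screening through Day 1". The passage beginning "Elevations of ALT or AST are defined as a baseline ALT or AST" gives two cases. A baseline below ULN counts as elevated above 3×ULN, and a baseline above ULN counts as elevated above 2×baseline. An elevation calls for a repeat test at 48–72 hours, notice to the Medical Monitor if it is confirmed and unexplained, and close observation. On dosing in that period, Table 2 says: "During the period of close observation, study drug can be continued if desired at the discretion of Corcept Medical Monitor and Investigator".

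**The concern.** The protocol detects a liver signal in a patient with normal baselines but does not say at what ALT or AST value dosing must end. A patient who starts just above ULN has such a value. A patient who starts at or below it has close observation and a decision left to two roles without a number.

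What is at stake is individual patient safety and consistency across about 15 sites. An asymptomatic patient with all-normal baselines could have a confirmed ALT or AST rise of any size and not meet a required stop on ALT or AST alone. Two sites could handle the same result differently and both be compliant.

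**Working it through.** The plan states no figure to reproduce here, so the check is to code the rules and see where they apply.

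**Can such a patient be enrolled?** Yes.

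- Section 4.1, criterion 3a(i), the route starting "A historical liver biopsy within 1 year of Screening showing NASH", sets no ALT or AST minimum.
- The AST floor (above 17 U/L in women, above 20 U/L in men) belongs to the non-invasive route only. No criterion sets an ALT floor.
- Inclusion 4 makes explicit provision for samples at or below 1.5×ULN. Exclusion 19 limits ALT and AST only from above.
- Exclusion 21c ("Total bilirubin >1.3 mg/dL (except for patients who have" Gilbert's syndrome) removes patients with raised bilirubin, which makes normal bilirubin the usual case.

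**Thresholds.** Let b be the baseline in multiples of ULN. The observation trigger is 3 for b < 1 and 2b for b > 1. The ALT/AST-alone stop is 5b for 1 < b < 2, 3b for 2 ≤ b < 5 and 2b for b ≥ 5. When all listed baselines have b ≤ 1, there is none.

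| Baseline (×ULN) | Observe above (×ULN) | Must stop above, ALT/AST alone (×ULN) |
|---|---|---|
| 0.5 | 3.0 | none |
| 0.9 | 3.0 | none |
| 1.0 | in neither definition | none |
| 1.01 | 2 × 1.01 = 2.02 | 5 × 1.01 = 5.05 |
| 1.5 | 2 × 1.5 = 3.0 | 5 × 1.5 = 7.5 |
| 2.0 | 2 × 2.0 = 4.0 | 3 × 2.0 = 6.0 |
| 5.0 | 2 × 5.0 = 10.0 | 2 × 5.0 = 10.0 |

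Of the five stopping bullets, three are ALT/AST-alone, and none of the three applies when all listed baselines are at or below ULN.

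**Would ignoring the header close the gap?** Bullet 1 would then give 5b for normal baselines: 5 × 0.3 = 1.5 and 5 × 0.5 = 2.5×ULN. Both lie below the 3×ULN observation trigger. The two meet at b = 3/5 = 0.6, so for lower baselines the patient would have to stop before being observed. Between 0.6 and 1.0 the result would be coherent (3 to 5×ULN).

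**Mixed baselines.** The header lists several analytes and does not say whether each is judged separately. Take AST 1.2×ULN and ALT 0.8×ULN. AST stops above 5 × 1.2 = 6.0×ULN on either reading. ALT stops above 5 × 0.8 = 4.0×ULN if the header qualifies the whole patient, and has no stop if it is read per analyte.

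**Could the combined bullet simply be extended to everyone?** No, because it uses baseline multiples. With ALT 0.4 and bilirubin 0.3×ULN, the cuts are 2 × 0.4 = 0.8 and 2 × 0.3 = 0.6×ULN. A move to 0.81 and 0.61 would force permanent discontinuation with both values normal.

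**The case against.** The strongest reply is that this discretion is structured. A rise above 3×ULN brings a repeat test, at-least-twice-weekly biochemistry and a decision by the Medical Monitor and the Investigator. The symptom bullet applies whatever the baseline. Section 4.4.1 allows discontinuation for unacceptable toxicity, Section 5.3.2 allows interruption, and Section 8.2 requires Grade 3 findings to be reported within 24 hours. All of this stands, and it rules out the stronger inference that these patients are unprotected. But none of these provisions gives an ALT or AST value at which dosing must end.

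The header can also be called an unclear boundary, since the last bullet under it is worded for any patients and bullet 1 has no lower bound. That supports clarifying the cell. It does not settle the matter, because dropping the header conflicts with the observation trigger below 0.6×ULN.

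The evidence has limits too. IDMC decision rules are placed in a charter, and monitoring details in a safety surveillance plan. Neither is available, so nothing is claimed about them. The public table may be incomplete: Section 5.3.3 lists "safety events (hyperkalemia; hypotension; excessive miricorilant" exposure among the events in Table 2, but no such row appears, and the footnote defines DILI, which the visible table does not use. The liver row itself shows no redaction mark.

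A 5×ULN line would be looser than one possible current reading: ALT in the mixed example would go from 4.0 to 5.0×ULN. That is fair, and it is a reason for clinicians to set the value.

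A reader might also see a conflict in potassium above 6.0 mEq/L being both a restartable interruption and a stop. Section 5.3.2 resolves that toward stopping, so it is not part of this point.

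**Conclusion.** The point holds for the published protocol body. A patient whose baseline ALT, AST and bilirubin are all at or below ULN has no required stop on ALT or AST alone, while a patient at 1.01×ULN has one at 5.05×ULN. For mixed baselines, the ALT rule depends on how a site reads the header.

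This rests on reading the header as written and on the public liver row being complete. The number of patients affected cannot be estimated, because neither the ULN values nor the baseline distribution is given.

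A reader might connect this gap with the early termination for safety-related observations reported in SAP Section 9.8. The SAP does not specify those observations, so the documents do not support that link.

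This is a cheap improvement in patient safety. It does not call any analysis into question.

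**What to change.** Make two changes in the liver stopping cell of Table 2.

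1. Add a line for baseline at or below ULN, judged per analyte, requiring a stop at a confirmed ULN multiple above the 3×ULN observation trigger. ALT or AST above 5×ULN is one candidate: it meets bullet 1 at b = 1 (5 × 1 = 5), and SAP Section 9.9.3 already tabulates that cut. In the mixed example, ALT would then stop above 5×ULN and AST above 6×ULN, with no ambiguity. The sponsor's clinicians should confirm the value.
2. For patients with all-normal baselines, state the combined stop in ULN multiples: for example, ALT or AST above 3×ULN with total bilirubin above 2×ULN (also tabulated in SAP Section 9.9.3), or with the INR rise of more than 0.2 from the existing bullet. Do not extend the baseline-multiple bullet to them.

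The cost is two added lines, with no change to sample size, visits, assessments or analyses. The downside is that a few patients who might have continued at discretion would have to stop. Because this trial has ended, the edit matters only if the table is used again.
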